## - Phase 2/3 Exclusion Criteria:

- 1. Cannot obtain informed consent.
- 2. Severe hepatic dysfunction (Child Pugh score  $\geq$  C, or AST> 5 times the upper limit); Severe renal dysfunction (estimated glomerular filtration rate  $\leq$  30mL / min / 1.73 m2) or receive continuous renal replacement therapy, hemodialysis, or peritoneal dialysis.
- 3. Patients with hypersensitivity to ibuprofen or to more than one non steroidal anti-inflammatory drug or to more than one medication belonging to the class of sulfonamides (e.g.

sulfamethazine, sulfamethoxazole, sulfasalazine, nimesulide or celecoxib; hypersensitivity to sulphanilamide antibiotics alone, e.g. sulfamethoxazole, does not qualify for exclusion)

- 4. Severe, active bleeding such as hemoptysis, gastrointestinal bleeding, central nervous system bleeding, and nosebleeds within 1 month before enrollment.
- 5. Pregnant and lactating women and those planning to get pregnant.
- 6. Participated in other interventional clinical trials with investigational medicinal products, not considered suitable for this study by the researchers.
- 7. At the time of enrollment, patients not in a clinical condition compatible with the oral administration of the study drug.

**Number of patients enrolled:** It is planned that 48 patients will be enrolled in Phase 2 and a total of 111 patients will be enrolled up to completion of the Phase 3. However, the sample size for the Phase 3 segment of this study may be re-estimated based on the Phase 2 results. In the current sample size scenario, 32 patients will receive Reparixin in Phase 2.

**Study duration:** treatment duration will be up to a maximum of 21 days. Overall Phase 2 study duration will be maximum 1 month (including 21 days of treatment and up to 7±3 days of follow-up).

**End of study (EOS) definition:** EOS is defined as the last day the last patient completes the last study assessment in the hospital, or retracts the consent to participate in the study, or withdraws from the study, or is deceased or otherwise lost to follow-up.

**Interventions:** Patients who satisfy the predefined inclusion and exclusion criteria for this trial will be randomized 2:1 to one of the following treatment groups:

- **GROUP 1:** Reparixin oral tablets 1200 mg TID for 7 days. **In case of improvement**, treatment can be prolonged at discretion of the investigator up to a maximum of 21 days of treatment in total or live discharge from the hospital, whichever comes first.

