### 4 STUDY DESIGN AND METHODOLOGY

#### 4.1 Phase 2 Study design

The study is designed for the investigational use of a CXCR1 and CXCR2 allosteric antagonist named Reparixin. It will involve 48 adult patients with severe COVID-19 pneumonia in accord with any of the following:

1. Age 18 to 90.

2. Confirmed COVID-19 diagnosis

3. At least one of the following: (1) Respiratory distress,  $RR \ge 30$  breaths/min without oxygen; (2) Partial arterial oxygen pressure (PaO2) / Fraction of inspiration O2 (FiO2) >100 <300mmHg (1mmHg = 0.133kPa).

4. Chest imaging confirms lung involvement and inflammation.

5. Inflammatory status as documented by at least one of the following: Lactate dehydrogenase (LDH) > normal range, C-reactive protein (CRP)  $\geq$  100mg/L or IL-6  $\geq$  40pg/mL, serum ferritin  $\geq$  900ng/mL, XDP >20mcg/mL.

Patients randomized to the active treatment will receive an oral dose of reparixin (1200 mg tablets TID) for 7 days. In case of improvement, treatment can be prolonged at discretion of the investigator up to a total of 21 days of treatment. Patients randomized to the both arms will be offered, in case of worsening (e.g. need of ICU and/or mechanical ventilation), a rescue medication based on their physicians' judgement, without any constrain from the sponsor.

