# 9 STATISTICAL CONSIDERATIONS

#### 9.1 Sample size

The sample size for this trial will be adaptively determined through a phase 2/3 design. Enrollment is planned to last approximately 2 months. Each patient will be randomly allocated to Reparixin or Control according to a randomization ratio of 2:1 and he/she will be followed for the entire treatment and follow-up duration for collecting the efficacy endpoints of each study phase.

For the Phase 2 portion of the study, the primary analysis will compare Reparixin versus Control in terms of time to a composite endpoint (primary endpoint of phase 2) including the following events: requirement of supplemental oxygen treatment, mechanical ventilation use, admission to ICU, and any requirement of rescue medication. Based on clinical experience, an improvement of the median time freedom from composite event of 1.5 times is expected. Assuming an exponential distribution, a total sample size of 48 patients will allow to provide 80% power to show superiority of Reparixin compared to control using a log-rank test at a one-sided significance level of 0.025.

The sample size for the phase 3 is based on assessment of superiority of Reparixin compared to control arm in terms of freedom from a composite endpoint (primary endpoint of phase 3) of severe events including death, admission to the ICU, requirement of mechanical ventilation.

Based on same assumptions of phase 2 regarding randomization (2:1) and expecting to double the median time freedom from severe composite event using Reparixin compared to control (from 2-4 to 4-8 days), a total sample size of 111 patients will allow to achieve a power of 90% to show superiority of Reparixin over control using a log-rank test at a one-sided significance level of 0.025. No drop-out are expected to happen. The number of patients to be included may be revised based on considerations from Phase 2 data analysis.

Primary endpoint of phase 3 will be tested only if superiority of Reparixin is shown in phase 2. Thus, the overall type I error of the study will be controlled at 0.025 via the hierarchical testing procedure.

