3.1 Visit Schedule and Visit Windows

Assessments and study visits will be performed as listed in Table 1. Paragraph no. 7 “Assessments and procedures” of Study Protocol contains additional details about scheduled visits, evaluations and assessments that are performed during the study.

Baseline is defined as the last visit prior to randomization. Unless otherwise specified, baseline values are defined as the measurements taken during this visit.

Table 1: Schedule of evaluations

Study procedures	Screening	Baseline	Day 1	Day 2	Week 1	End of treatment	End of follow up
Informed Consent	X						
Inclusion/Exclusion Criteria	X	X					
Pregnancy Test	X						X
Randomization		X					
Demographics	X						
Medical History	X						
Previous And Concomitant Medications	X	X	X	X	X	X	X
Clinical severity score	X	X	X	X	X	X	X
Liker scale	X	X	X	X	X	X	X
Dyspnea VAS scale	X	X	X	X	X	X	X
Body temperature	X	X	X	X	X	X	X
Hematology evaluations*	X	X	X	X	X	X	X
Oxygen treatment (time and quantity)	X	X	X	X	X	X	X
Mechanical ventilation (Yes/No)	X	X	X	X	X	X	X
ICU admission (Yes/no)	X	X	X	X	X	X	X
Chest radiologic imaging	X	X§	X§	X§	X§	X	X§
PaO ₂ , SpO ₂ , FiO ₂	X	X	X	X	X	X	X
CRP, Hs-CRP	X	X	X	X	X	X	X
Cytokine profile **	X	X	X	X	X	X	X
Reparixin blood concentration **			X	X	X	X	X
SARS-CoV-2 virologic counts **		X			X	X	X
Study drug dispensation		X					
Verify study medication dosing compliance			X	X	X	X	
Record AEs / SAEs	X	X	X	X	X	X	X

* Including routine hematology as for local laboratory procedures and predefined hematochemical evaluations required for this study;

** Not mandatory; § When deemed appropriate by the investigators.

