3.2 Sample size justification

The sample size of the full phase 2/3 study is calculated based on data from clinical experience and on Sponsor expectations as reported in Table 2:

Table 2: Assumptions for primary endpoints

Primary endpoint*	Standard of care (control)	Reparixin
Time to primary endpoint of phase 2	2 days	5 days
Time to primary endpoint of phase 3	2-4 days	4-8 days

* see section 3.5.1.

Based on the following assumptions:

- an enrollment phase of 2 months,

- a total follow-up of 21 days,
- a randomization ratio (reparixin:control) of 2:1
- an exponential distribution for survival probability $S(t) = e^{-\lambda t}$,
- a comparison between treatment by means of a log-rank test,
- an interim analysis framework as described in section 4.5, and
- a correction of the type I and II errors by means of O'Brien-Fleming spending functions

a total of 109 events (corresponding to approximately 111 subjects) will allow to provide >80% power to show superiority of reparixin vs standard of care in terms of primary endpoint of phase 3, controlling the type I error under 0.025.

Based on the same assumptions reported above, phase 2 portion of the study will be performed when a total of 46 events (corresponding to approximately 48 subjects) has happened. This allow to achieve approximately 80% power to show superiority of reparixin vs standard of care in terms of (not severe) primary endpoint of phase 2, controlling the type I error under 0.025.

The remaining portion of the 111 patients will be enrolled in the phase 3 study segment. Anyhow, due to the novel nature of the COVID-19 pandemic and being the primary efficacy endpoint planned in phase 3 not well established, it may require confirmation based on phase 2 data. For this reason, at the end of the phase 2 portion, power calculations may be reassessed, and sample size may be re-estimated for phase 3.

The adaptive design allows for the assessment of efficacy endpoint in phase 2 which are then seamlessly confirmed in the phase 3. Since primary endpoint of phase 3 will be tested only if superiority of reparixin is shown in phase 2 (at interim or final stage), the overall type I error of the study will be controlled at 0.025 via the hierarchical testing procedure.

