7.2.2 Comparison between treatments

Along with the above summary statistics, comparisons between treatments will be performed as detailed in the next sub-sections. Parametric test (i.e. two-sample t-test for continuous variables, Chi-square test for categorical) will be adopted as first choice. In case the required assumptions are not met, the corresponding non-parametric counterpart will be used (i.e. the two-sample Mann–Whitney U test for continuous variables, and the Fisher’s Exact test for the categorical). Normality of continuous data is assessed by Kolmogorov-Smirnov test.

Comparison will be performed at each available time point, where applicable. Any exception will be declared.

7.2.2.1 *Composite endpoint of phase 2 using Oxygen Delivery System Classification*

The composite endpoints will be summarized along with their single component by a binomial response rate at each time point (only the first event will be considered). The Clopper-Pearson method will be used to estimate the two-sided 95% CIs.

Time to composite endpoint(s) will be performed using the KM methodology and the one-sided log-rank test will be used to test for differences between treatment groups.

7.2.2.2 *Changes in clinical severity score*

Number and proportion along with the 95% confidence interval (Clopper-Pearson’s formula) of subjects with a clinical severity score improvement of at least two points compared to randomization or live discharge from the hospital will be calculated and compared.

7.2.2.3 *Dyspnea severity (Liker scale and VAS scale)*

The comparison of the Liker scale between the two study treatment arms will be performed by means of Wilcoxon signed-rank test, given its ordinal nature.

Number and proportion along with the 95% confidence interval (Clopper-Pearson’s formula) of subjects with

any improvement (improved vs not-improved) will be calculated and compared.

VAS scale comparison between treatments will be performed according to its continuous nature.

7.2.2.4 *Changes in body temperature*

Comparison between treatments in change from baseline of the body temperature will be performed according to the continuous nature of the variable.

7.2.2.5 *Incidence of supplemental oxygen treatment*

Number and proportion along with the 95% confidence interval (Clopper-Pearson's formula) of subjects who worsened according to PaO₂/FiO₂ and to Oxygen Delivery System Classification based on oxygen support will be calculated and compared.

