At each time point the number and proportion of patients within each class (Severe, Moderate, or Mild for PaO₂/FiO₂; Invasive, High Flow, or Low Flow for the type of support) will be provided.

Finally, summary of cumulative quantity (L) and cumulative duration (hours) of oxygen treatment will be performed at 7 days and subsequent time points considering the variable as continuous.

7.2.2.6 *Incidence and duration of mechanical ventilation use*

Number and proportion along with the 95% confidence interval (Clopper-Pearson's formula) of subjects requiring mechanical ventilation will be calculated and compared.

Comparison between treatments in cumulative duration (hours) of mechanical ventilation will be performed at 7 days and subsequent time points considering the variable as continuous. Analysis will be performed overall and stratified by Invasive/Non-invasive mechanical ventilation.

7.2.2.7 *Incidence of ICU admission need*

Number and proportion along with the 95% confidence interval (Clopper-Pearson's formula) of subjects requiring ICU admission will be calculated and compared.

Comparison between treatments in duration (days) of ICU stay will be performed considering the variable as continuous.

7.2.2.8 *Change from baseline in lung damage extension and lung exudation degree (assessed by Chest CT or Rx)*

The comparison of the clinical evaluation of lung damage extension and lung exudation between the two study treatment arms will be performed by means of Wilcoxon signed-rank test.

7.2.2.9 *Respiratory parameters*

Change from baseline of FiO₂, Respiration rate, PaO₂, SpO₂ and PaO₂/FiO₂ will be compared between treatments considering the continuous nature of these variables.

7.2.2.10 *CRP and Hs-CRP*

CRP (mg/L) and Hs-CRP (mg/L) will be compared between treatments considering their continuous nature.

7.3 **Analysis of exploratory efficacy endpoints**

Explorative endpoints (section 3.5.3) will be analyzed at each available time points by means of descriptive statistics. Specifically, analyses will be provided for baseline visit, each post-baseline visit, and the change from baseline measurements to each visit. Comparison between treatments will be performed by means of two-sample t-test or, if assumptions of normality is not confirmed (by Kolmogorov-Smirnov test), two-sample Mann-Whitney U test.

In case of different units of measure considered for the same laboratory parameter, all values will be converted

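### End of treatment and End of follow-up have no study day, so alignment of the arms at these two visits is not assured, yet SAP 7.2.2 compares the arms there

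*SAP*

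**What the plan says.** - **Visits.** SAP 3.1 states: "Assessments and study visits will be performed as listed in Table 1". That table runs Screening, Baseline, Day 1, Day 2, Week 1, End of treatment, End of follow up. The last two carry no day, and despite its title the section gives no windows. It refers to Protocol section 7, which it says "contains additional details about scheduled visits, evaluations and assessments that are performed during the study". Protocol 7.1 and 7.4 give only a ceiling of 31 days and say that patients stay in the study throughout hospital treatment.
- **Reparixin course.** Protocol 4.1 sets 7 days and adds: "In case of improvement, treatment can be prolonged at discretion of the investigator up to a total of 21 days of treatment". The Protocol Summary also ends the extension at live discharge.
- **Control course.** Protocol 6.2 says that standard of care cannot be fixed in advance. SAP 5.4 and 6.1 record whether it continues and for how many days, but nothing defines its end.
- **Follow-up after treatment.** The Protocol Summary describes the maximum phase 2 duration as "including 21 days of treatment and up to 7±3 days of follow-up".
- **Comparisons.** SAP 7.2.2: "Comparison will be performed at each available time point, where applicable". Under 7.2.2.5, a summary of cumulative quantity and duration of "oxygen treatment will be performed at 7 days and subsequent time points considering the variable as continuous"; 7.2.2.6 compares cumulative ventilation hours at the same points. SAP Table 7 sums both from randomization to the visit in question.
- **Efficacy follow-up.** SAP 3.2 assumes "a total follow-up of 21 days", and the statistical plan in the Protocol Summary also gives 21 days. Protocol 9.1 instead has each patient "followed for the entire treatment and follow-up duration for collecting the efficacy endpoints of each study phase".

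**The concern.** In the reparixin arm, the date of End of treatment depends on a response seen after randomization and judged open-label. In the control arm no rule sets it. Comparing the arms at that visit mixes any drug effect with the day of illness on which each patient happens to be measured. This affects PaO2/FiO2, CRP, the dyspnea VAS, the severity score and imaging. Cumulative oxygen and ventilation are affected more directly, because a longer window gives a larger total. If no rule is written down, the timing of these comparisons can be settled after data from an open-label trial have been seen.

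**Working it through.** **1. The plan's own figure.** Maximum participation: 21 days of treatment + 7 + 3 days of follow-up = 31 days, which agrees with Protocol 7.1.

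**2. Range of the two visits in the reparixin arm.** End of treatment falls between day 7 and day 21. If the same 7±3 days follow a 7-day course, End of follow-up falls between day 7 + 7 − 3 = 11 and day 21 + 7 + 3 = 31. The lower end is an inference, because the protocol gives 7±3 days only when describing the maximum duration. For controls neither range can be computed.

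**3. Window length at End of treatment.** Assume that a share q of reparixin patients is extended to day 21 and the rest stop at day 7. The mean window is 7 + 14q days. The documents give neither q nor the control day, so both are varied.

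| q | Mean reparixin window (days) | Ratio if controls at day 7 | Ratio if controls at day 21 |
|---|---|---|---|
| 25% | 10.5 | 10.5/7 = 1.5 | 10.5/21 = 0.50 |
| 50% | 14.0 | 14/7 = 2.0 | 14/21 = 0.67 |
| 75% | 17.5 | 17.5/7 = 2.5 | 17.5/21 = 0.83 |

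With constant use and no drug effect, mean cumulative hours follow these ratios. Which arm looks worse depends on the unstated control rule.

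**4. Effect on a test at End of treatment when the drug does nothing.** This is a simulation under assumed values, with 32 versus 16 patients, a two-sided t-test at 0.05 and 20,000 runs per scenario. Change from baseline = slope × visit day + error. The error SD is 1; slopes are normal with mean μ and SD 0.07 error-SDs per day. The share q with the better slopes is extended to day 21. Entries are rejection rates.

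| μ | q | Controls at day 7 | Controls at day 21 |
|---|---|---|---|
| 0 | 25% | 0.087 | 0.113 |
| 0 | 50% | 0.132 | 0.141 |
| 0 | 75% | 0.081 | 0.109 |
| 0.05 | 25% | 0.135 | 0.080 |
| 0.05 | 50% | 0.326 | 0.058 |
| 0.05 | 75% | 0.436 | 0.063 |
| 0.10 | 25% | 0.190 | 0.259 |
| 0.10 | 50% | 0.549 | 0.081 |
| 0.10 | 75% | 0.813 | 0.049 |

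The sign of the bias can reverse: at μ = 0.10 and q = 25%, the mean difference (reparixin minus control) is +0.66 with controls at day 7 and −0.74 with controls at day 21. With both arms measured at a common day 7 or day 21, the rejection rate is 0.048 to 0.054. If controls followed a mirrored extension rule, which the documents do not contain, it would be 0.049 to 0.052.

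**5. Primary endpoints.** The log-rank analysis runs on time from randomization and does not compare arms at a visit. Two indirect routes remain. SAP Table 7 dates ICU admission by the visit, and also PaO2/FiO2 worsening (a phase 2 component), so undefined visit days enter the event times. The follow-up horizon is also stated in two ways: 21 days (Protocol Summary, SAP 3.2) and treatment plus follow-up (Protocol 9.1).

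**The case against.** The documents do not say that controls are seen on different days. The SAP records standard-of-care treatment days, so it presumes a control treatment end, and the case report form, which is not among these documents, may date it. This stands, and it is why the point is that alignment is not assured, not that the arms are misaligned. The scope is also limited. Day 1, Day 2 and Week 1 are common to both arms, the cumulative analyses include a fixed 7-day point, oxygen totals are described as a summary, and SAP 7.1.3 bases the decision to proceed to phase 3 on the primary analysis alone. None of this supplies the missing day for the two later visits.

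A reader might infer more than the text supports:

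- **Informative censoring confined to the reparixin arm.** Protocol 7.1 and 7.4 keep each patient in the study throughout hospital treatment, and the Protocol Summary follows everyone for 21 days for efficacy. Extension also stops at live discharge, so improvers may be the ones who leave early. Neither the existence nor the direction of such censoring is established.
- **A shortfall of phase 2 events.** At medians of 2 and 5 days, 16(1 − 2^(−L/2)) + 32(1 − 2^(−L/5)) gives 43.3 events at L = 14 and 46.2 at L = 21. The lower figure puts all 48 patients, controls included, on a 7-day course. The planned 46 does not single out 21 days either: L = 19 gives 45.7 and L = 20 gives 46.0.
- **A loss of 14% of phase 3 reparixin events after day 14.** This takes the 8-day median (29.7% − 16.2%); at 4 days it is 8.8% − 2.6% = 6.2%. It also borrows the phase 2 course, whereas Protocol 6.1 leaves the phase 3 duration to be decided.
- **A general 3-fold difference in cumulative hours.** This needs every control at day 7, every reparixin patient at day 21 and constant use.

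**Conclusion.** The point holds for the secondary comparisons at End of treatment and End of follow-up. As written, the plan compares the arms at visits whose day depends on response in one arm and is undefined in the other. Window ratios of 0.50 to 2.5 at End of treatment follow from extending 25% to 75% of reparixin patients and placing controls at day 7 or day 21. Under the simulation's assumptions, the null rejection rate is 0.08 to 0.81 with controls at day 7 and 0.05 to 0.26 with controls at day 21. These figures illustrate what the missing rule permits. They are not estimates for this trial, and the documents do not fix the direction. For the primary analyses, the conclusion is limited to visit-dated components and a follow-up horizon that must be reconciled; no size is claimed.

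**What to change.** - In SAP 3.1, define analysis days and windows counted from randomization and identical in both arms: Day 1, Day 2, Week 1 and day 21.
- In SAP 7.2.2, make between-arm comparisons only at those days, and report End of treatment descriptively.
- In SAP 7.2.2.5, 7.2.2.6 and Table 7, compute cumulative oxygen and ventilation over 0–7 and 0–21 days for everyone.
- Reconcile the 21 days in the Protocol Summary and SAP 3.2 with Protocol 9.1, so that each primary endpoint has one follow-up horizon, the same in both arms.

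No change to treatment duration is proposed. Day 21 is already the horizon in the sample-size assumptions and lies within the 31 days allowed. The cost is more than wording: day-21 status must be obtained for some patients after a short course or after discharge. For phase 3 the change can go into the protocol amendment and SAP update that SAP 4.7 already requires.

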### - Phase 2/3 Study Endpoints:

- **Primary Endpoint for Phase 2:** Composite endpoint of clinical events (the patient requires at least one of the following: supplemental oxygen requirement, mechanical ventilation use, admission to ICU, and use of a rescue medication for any reason)
- **Primary Endpoint for Phase 3:** Composite endpoint of death and clinical severe events (the patient dies or requires mechanical ventilation use and/or admission to ICU)
- Secondary Endpoints:
  - Changes in clinical severity score (as recommended by WHO for COVID studies), defined as the time to clinical improvement of two points from the time of randomization on a seven-category ordinal scale or live discharge from the hospital, whichever comes first. The seven-category ordinal scale consists of the following: 1) not hospitalized, with resumption of normal activities; 2) not hospitalized, but unable to resume normal activities; 3) hospitalized, not requiring supplemental oxygen; 4) hospitalized, requiring supplemental oxygen; 5) hospitalized, requiring high-flow oxygen therapy, noninvasive mechanical ventilation, or both; 6) hospitalized, requiring ECMO, invasive mechanical ventilation, or both; and 7) death.
  - Dyspnea severity (Liker scale and VAS scale)
  - Changes in body temperature
  - Changes hematology test values
  - o Duration and quantity of supplemental oxygen treatment
  - Incidence and duration of mechanical ventilation use
  - o Incidence of intensive care unit (ICU) admission need
  - Lung damage extension changes from baseline (assessed by Chest CT or Rx)
  - Change from baseline in lung exudation degree (assessed by Chest CT or Rx)
  - o PaO2
  - o SpO2
  - Partial arterioral oxygen pressure (PaO2) to fraction of inspiration O2 (FiO2) ratio
  - o CRP
  - o Hs-CRP

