3.5 Efficacy endpoints

3.5.1 Primary endpoints

- Primary Endpoint for phase 2: Composite endpoint of clinical events (the subject requires at least one of the following: supplemental oxygen requirement, invasive mechanical ventilation use, admission to ICU, and use of a rescue medication for any reason);
- Primary Endpoint for phase 3: Composite endpoint of death and clinical severe events (the subject dies or requires invasive mechanical ventilation use and/or admission to ICU).

3.5.2 Secondary Endpoints:

- Clinical severity score (a seven-category ordinal scale) at any available time point
- Dyspnea severity (Liker categorical scale and VAS continuous scale) at any available time point;
- Changes in body temperature at any available time point;
- Duration and quantity of supplemental oxygen treatment at any available time point;
- Incidence and duration of mechanical ventilation use at any available time point;
- Incidence of ICU admission need at any available time point;
- Lung damage extension changes from baseline (assessed by Chest CT or Rx) at any available time point;
- Change from baseline in lung exudation degree (assessed by Chest CT or Rx) at any available time point;
- PaO₂ at any available time point;
- SpO₂ at any available time point;
- Partial arteriolar oxygen pressure (PaO₂) to fraction of inspiration O₂ (FiO₂) ratio at any available time point;
- CRP at any available time point;
- Hs-CRP at any available time point;

3.5.3 Exploratory Endpoints (not mandatory):

- Cytokine profile at any available time point;

- Concentration of reparixin in serum over time;
- SARS-CoV-2 virologic counts at any available time point.

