4.1 General

Appropriate descriptive statistics will be produced, according to the variable:

- for continuous data n , mean, standard deviation (SD), median, Q1-Q3, and range (minimum and maximum) will be presented;
- for categorical data, frequency distributions and percentages will be presented;
- for time-to-event variables, cumulative freedom from event will be evaluated using Kaplan-Meier (KM) method. The degree of uncertainty will be expressed with 95% confidence limits (calculated per the method proposed by Greenwood³). Comparison of curves among arms will be performed with the log-rank test. KM graphs will be presented along with the number of subject-at-risk at exact time points. Subjects who have discontinued/terminated the study without an event will be censored at the date of study discontinuation/termination. Subjects ongoing and who are free from event at the time of database lock (for example at interim analyses) will be censored at the last available date.

Unless otherwise specified, hypothesis testing will be carried out at the $\alpha = 0.050$ level (two-sided) when comparing treatments. For all inferential analyses, p-value will be rounded to three decimal places. Statistical significance will be declared if the rounded p-value will be less than or equal to 0.050. For primary analysis only (section 7.1.2), p-values will be provided at 5th decimal place, in order to compare with efficacy and futility thresholds specified in section 4.5.

Additional post-hoc analysis may be produced to further allow comparison between reparixin and control, according to the results obtained. Any unplanned analyses as well as deviations from the original statistical plan will be clearly documented in the Clinical Study Report.

Derivation rules for efficacy and safety analyses are reported in Table 7 in section 9.

All the data collected and derived in the study will be presented in subject data listings by centre.

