4.9 Changes in the planned analysis

No change has been implemented in this SAP.

However, in order to clarify the analysis of the primary endpoint, a clarification of the meaning of "supplemental oxygen treatment" is provided: since all patients enrolled in this study had a respiratory distress, it is intended in all the analysis that the term "supplemental" refers to additional and/or increased oxygen requirement as compared to the baseline. In fact, all patients were expected to be already on oxygen treatment before the start of treatment. Details are provided in section 9.1.

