7.2 Analysis of secondary efficacy endpoints

7.2.1 Descriptive Analysis

Descriptive in nature analyses will be performed on all secondary endpoints (section 3.5.2) at each available time points by means of descriptive statistics (section 4.1).

In case of continuous measures, analyses will be provided for:

- baseline visit,
- each post-baseline visit, and
- the change from baseline measurements to each visit.

In case of categorical variables, shift tables showing difference as to the respective classifications at baseline might be provided.

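### The SAP replaces the protocol's time to two-point improvement or live discharge with visit-by-visit responder proportions, and declares no change

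*SAP*

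**What the plan says.** Protocol section 3 lists changes in clinical severity score among the secondary endpoints, "defined as the time to clinical improvement of two points from the time of randomization on a seven-category ordinal scale or live discharge", whichever of the two comes first. The protocol synopsis names the endpoint without this definition.

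SAP 3.5.2 lists it as "Clinical severity score (a seven-category ordinal scale) at any available time point". SAP 7.2.2.2 keeps the protocol's event but analyses it as a count and proportion, with a Clopper-Pearson interval, of "subjects with a clinical severity score improvement of at least two points compared to randomization or live discharge from the hospital". SAP 7.2.2 sets the timing ("Comparison will be performed at each available time point, where applicable") and the default tests ("two-sample t-test for continuous variables, Chi-square test for categorical"), with Fisher's exact test as the fallback for categorical data. SAP 7.2.1 adds descriptive statistics and says that "shift tables showing difference as to the respective classifications at baseline might be provided".

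On departures from the protocol, SAP 4.9 says "No change has been implemented in this SAP". Its one clarification concerns supplemental oxygen.

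**The concern.** The protocol's variable is a time, and the SAP's variable is a yes/no status at each visit. They share an event but answer different questions: how soon patients improve, and how many have improved by a given visit.

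Two things are at stake. First, an analysis team working from the SAP would produce no estimate of the endpoint that the protocol defines. Second, a reader of SAP 4.9 would believe that the protocol's endpoints had been carried over intact. The trial is open-label, so an undeclared change of endpoint is a matter of credibility whatever its effect on power.

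**Working it through.** **Text comparison**

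| Place | What it gives for this endpoint |
|---|---|
| Protocol 3 | Time from randomization to a two-point improvement or live discharge |
| Protocol 9.4.1 | Kaplan-Meier and log-rank for time-to-event variables |
| Protocol 9.4.2.5 | Leaves the choice of test to the nature of the variable, with details in the SAP |
| SAP 3.5.2 | Score at each time point |
| SAP 7.2.2.2 | Responder number and proportion, compared between arms |
| SAP Table 7 | Times to oxygen, ventilation, ICU, rescue and death, but none to improvement or discharge |
| SAP 4.9 | No change |

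SAP 4.1 does say that "for time-to-event variables, cumulative freedom from event will be evaluated using Kaplan-Meier (KM) method". That rule needs a variable defined as time-to-event, and the SAP neither defines nor derives one here. SAP 7.2.2.1, immediately before, names Kaplan-Meier and log-rank for another secondary analysis, so the SAP says so where it wants that comparison. Protocol 9.4.2.5 lets the SAP choose a test. It does not provide for changing the type of variable.

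**Size of any power loss**

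The documents give no sample size, effect or power for this endpoint, so there is no figure to reproduce. From the documents: 2:1 allocation, N = 48 or 111, two-sided 0.05, and a 21-day follow-up (SAP 3.2). Assumed: exponential times, control median m of 10–14 days, improvement rate ratio r of 1.8–2.0, no deaths or dropout.

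Proportion improved by day t: control 1 − 0.5^(t/m), reparixin 1 − 0.5^(rt/m).

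One scenario by formula, with N = 111 (74 and 37), m = 14, r = 1.8:

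- Day 7: control 1 − 0.5^0.5 = 0.293; reparixin 1 − 0.5^0.9 = 0.464.
- Day 21: control 1 − 0.5^1.5 = 0.646; reparixin 1 − 0.5^2.7 = 0.846.
- Log-rank (Schoenfeld): events = 37 × 0.646 + 74 × 0.846 = 86.5. Power = Φ(√(86.5 × 2/9) × ln 1.8 − 1.96) = Φ(0.62), about 73%.
- Two-proportion test: power = Φ((difference − 1.96 × pooled SE)/unpooled SE). Day 7: Φ((0.171 − 0.194)/0.095), about 40%. Day 21: Φ((0.200 − 0.164)/0.089), about 66%.

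Schoenfeld's formula runs a few points high here; the lower end of the simulated log-rank range is 70%.

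Simulated power over the assumed ranges (2,000 runs per scenario):

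| Analysis | N = 48 | N = 111 |
|---|---|---|
| Log-rank, exact times | 36–52% | 70–89% |
| Log-rank, scores read only on days 1, 2, 7, 21 (assumed grid) | 35–49% | 67–85% |
| Proportion at day 7 | 20–35% | 40–68% |
| Proportion at day 21 | 35–49% | 66–79% |

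Compared scenario by scenario, exact-time log-rank gains about 14–30 points over the day-7 proportion and about 0–12 over the day-21 proportion. On the assumed visit grid, the difference from day 21 is about −3 to +9.

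The late-visit result depends on not everyone having improved. In a separate set of runs with daily resolution, 95% of controls improved by day 28 (a median of 28 × ln 2/ln 20 = 6.5 days). There, at N = 111 and a rate ratio of 2.0, power was 90% for log-rank and 48% for the day-28 proportion.

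**The case against.** A reader might infer that the SAP throws away all timing, at a heavy cost in power on the trial's main clinical secondary outcome. The documents do not support that.

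- **Timing.** Proportions at Day 1, Day 2, Week 1, end of treatment and end of follow-up keep coarse timing. The score is scheduled only at those visits after baseline, so dates of a two-point change are themselves visit-grained. What is lost is the order and date of first events and the handling of censoring. End of treatment is also not a common time, since treatment runs from 7 to 21 days by patient.
- **Power.** A large loss appears if the week-1 proportion is the only comparator. The SAP compares at every visit, and under the main assumptions a late visit loses little. Every median and rate ratio above is assumed.
- **Importance.** The secondary endpoints are neither ranked nor powered. Being listed first is not a hierarchy.
- **Delegation.** Protocol 7.2 and 9.4.2.5 leave assessment and test details to the SAP. That covers the choice of test, but does not clearly cover replacing the endpoint.
- **Consequence.** The primary tests are untouched, and SAP 7.1.3.1 bases the decision to proceed to phase 3 on the primary analysis alone.

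These points limit the size of the concern. None of them removes the mismatch or the statement that nothing changed.

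**Conclusion.** The discrepancy stands on the text alone. A secondary endpoint that the protocol defines as a time would not be reported, and the SAP does not disclose this. It should be corrected, but it does not threaten the primary conclusions or their type I error.

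Power supports the correction without carrying it. Under exponential times, a control median of 10–14 days and a rate ratio of 1.8–2.0, the loss is large at week 1 (about 14–30 points) and small at a late visit (about 0–12, or −3 to +9 on the assumed visit grid). Faster recovery in the control arm would make a late proportion less informative. The documents do not say which case applies.

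**What to change.** Add to SAP 7.2.2.2 and Table 7 the time from randomization to the first recorded two-point improvement or live discharge, whichever is earlier. Analyse it by Kaplan-Meier and log-rank, as protocol 9.4.1 requires for time-to-event variables. Keep the visit proportions as supportive.

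Three details go beyond the protocol and are recommendations only:

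- State one fixed horizon. SAP 3.2 gives a follow-up of 21 days, while protocol 7.1 allows up to 31 days including follow-up.
- Keep patients who die as not improved to that horizon. Under SAP 4.1 they would be censored at termination, which for an improvement endpoint treats a death as if the patient could still have recovered.
- A hazard ratio with its interval may be added.

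If the sponsor prefers the proportion, SAP 4.9 should declare the change and give the reason.

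The cost is one derivation and one analysis. Improvement dates will be limited to scheduled visits. A discharge date must be available in the CRF; the schedule of evaluations does not list one, so this needs checking.
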